**Transcranial Photobiomodulation for
reducing autism symptoms in
children.**

October 1, 2020

PROTOCOL TITLE:

Transcranial photobiomodulation for reducing autism symptoms in children.

PRINCIPAL INVESTIGATOR:

Name	[name]
Department	N/A
Phone Number	

CO-INVESTIGATORS:

Name	[name]
Department	N/A
[contact]

Name	[name], CFA, Esq.
Department	N/A
[contact]

1.0 Purpose of the study:

The purpose of this 8-week open label feasibility study is to assess the tolerability, safety and efficacy of Transcranial LED Therapy for language learning and reducing symptoms of autism in children.

The investigators propose to enroll up to 30 participants of both genders ages 24 months to 6 years who have been previously diagnosed with moderate to severe ASD by licensed professionals according to the Diagnostic and Statistical Manual of Mental Disorders, Fifth Edition (DSM-5) criteria for Autism Spectrum Disorder (ASD).

The hypothesis to be tested is that exposure to photobiomodulation and speech parsing program will reduce children's symptoms of autism, such as delays in language production and comprehension, anxiety, tantrums, limited eye-contact and improve responsiveness.

2.0 Background / Literature Review / Rationale for the study:

2.1 Background Science of Photobiomodulation and Rationale:

There are several studies that suggest that mitochondrial energy disturbance is an underlying mechanism of autism, for at least some of the children. Specifically, Weisman, Kelley, Bauman, Cohen, Murray, Mitchell and Kern (2008) looked at the medical records of 25 children diagnosed with autism and found that "Levels of blood lactate, plasma alanine, and serum ALT and/or AST were increased at least once in 76%, 36%, and 52% of patients, respectively". Furthermore, 2 out of those 25 people had rare mtDNA mutations. The authors concluded that at least for a subset of ASD children, mitochondrial disturbances in energy production could be the underlying mechanism. Furthermore, Giulilvi, Zhang, Omanska-Klusek, Ross-Intra, Hertz-Picciotto, Tasson and Pessach (2010), looked at biochemical markers of ASD kids (2-5yo), and concluded that ASD children are more likely to have Mitochondria dysfunction, mtDNA replication and mtDNA deletion than neurotypical ones.

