We are developing a safe and effective protocol for administering tPBM via a wearable device. This physical device is getting developed by JelikaLite LLC. The parameters are developed by [name] (the PI of this study), [name] (leading photobiomodulation expert from Harvard Medical School and an advisor to JelikaLite), [name] (leading neuroscientist who is studying photobiomodulation at Boston Medical University and an advisor to JelikaLite), and [name] (an industrial product designer with over 30 years of expertise in designing medical devices). The purpose of this feasibility study is to evaluate the safety and comfort of the product, as well as preliminary efficacy of the treatment effect. The device will stimulate Default Mode Network (to increase brain connectiveness) as well as Broca and Wernike areas (to facilitate speech comprehension and production) and Occipital lobe (as many ASD children rely on visual information for language learning). The device will be physically light, comfortable to wear for children and could eventually be used at home as frequently as necessary.

The reason why the device may be helpful to children is because of the science of photobiomodulation. The device will have embedded LED lights in it, which will shine red light and near infra red lights. The children will wear the device for approximately 5-10 minutes, twice a week (closely replicating the protocol of Leisman et al as well as the clinical study at MGH). The light stimulates mitochondrial ATP production. Only about 2% of the light penetrates the skull. However, because brain is the largest energy consuming organ of the body, even those 2% result in significant

improvement of the symptoms (even small boost in ATP production results in significant improvement). Having more energy enables the brain cells to heal, grow and form new neural connections. Other benefits of tPBM is increased blood flow to the brain, which increase brain oxygen supply and reduce inflammation.

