1. Participant child is experiencing severe self-injurious behavior or severe aggressive behavior to self or others (within past 7 days).
2. Participant has been diagnosed with another psychiatric or neurological disorder (e.g. epilepsy) or have exhibited symptoms of major psychiatric disorders within the last 30 days.
3. Participant has an unstable medical condition (that requires clinical attention).
4. Participant has a significant skin condition at the procedure sites (i.e., hemangioma, scleroderma, psoriasis, rash, open wound or tattoo).
5. Participant has an implant of any kind in the head (e.g. stent, clipped aneurysm, embolised AVM, implantable shunt - Hakim valve).
- 6. Participant has receiving medication on a regular basis for Autism or any other medical condition.**
7. Any use of light-activated drugs (photodynamic therapy) within 14 days prior to study enrollment (in US: Visudine (verteporfin) - for age related macular degeneration; Aminolevulinic Acid- for actinic keratoses; Photofrin (porfimer sodium) - for esophageal cancer, non-small cell lung cancer; Levulan Kerastick (aminolevulinic acid HCl) - for actinic keratosis; 5-aminolevulinic acid (ALA)- for non-melanoma skin cancer).
8. Current treatment with a psychotropic medication.
9. Investigator and his/her immediate family, defined as the investigator's child or grandchild.

5.0 Sample Size:

30 children will be included in the study. We need at least 15 participants in the control condition, and 15 participants will receive a combined light and audio treatment therapy. These numbers will allow us to gain sufficient statistical power to detect small size systematic effect. **We anticipate to screen about 40 participants to recruit 30 participants for the study.**

We plan to screen more than 30 prospective children, because we expect some of them to be ineligible for the study, due to the above listed Exclusion Criteria. We plan to enroll 30 children, so that each group will have at least 15 participants. We do anticipate that some of the participants will withdraw, for various reasons. participant We will continue screening until we have 30 enrolled participants.

If a participant drops out of the Study we will attempt to replace that participant, using the same Eligibility Screening Criteria.

6.0 Research Locations:

[name]

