This is a private professional office, with a waiting room and a receptionist. There are several private rooms within the office.

The child will be led to a private room, which will have toys and books inside it. The caregiver and one of the researchers will be present in the room at all times.

[name]

This is a private professional office, with a waiting room and a receptionist. There are several private rooms within the office.

The child will be led to a private room, which will have toys and books inside it. The caregiver and one of the researchers will be present in the room at all times.

7.0 Procedures Involved:

7.1 Location: The study will use pre-test and post-test design. The entire study on the children will be done in the office. The weekly interview with the parent may be done either in office or by phone, as preferred by the parent.

7.2 Conditions: There are two conditions: placebo condition, and combined light and audio therapy treatment condition. The placebo control condition will listen to nursery rhymes. **The placebo control condition will wear the same device, however the lights are not going to be turned on. Otherwise, all experience for participants in control and experimental conditions will be identical.**

This study replicates and extends previous studies of photobiomodulation in children older than 5 years of age (Leisman et al, 2018).

7.3 Participants: The participants will be matched on age, gender and number of hours of therapy they receive independent from the study. The participants will be 24-71 month old children previously diagnosed with moderate or severe ASD. The experiment will use random assignment. We plan to use 30 participants (15 in each group). **We plan to screen about 40 participants (or fewer) to recruit the 30 participants for this study.**

7.4 Random Assignment: Random assignment will be achieved by using random number generator programs frequently used in research (such as random.org). Each participant is assigned a number. The list of 30 numbers is entered into the program, which creates a random sequence of 30 participants. Here is an example of the beginning of such list generated for 30 participants

1 – 23

2 – 25

1 – 12

2 – 15

1 – 21

2 – 5

1 – 19

2 - 9

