Once the program generates the random sequence of 30 participants (in the example above, the sequence goes 23, 25, 12, 15, etc), we will simply alternate the assignment to treatment and control conditions. For example, in the example above, participant number 23 is assigned to the treatment condition (1), and participant number 25 is assigned to the control condition (2). Because the sequence of the participants is randomized, the assignment to conditions is random.

7.5 Treatment: The treatment will take place twice a week for up to 30 minutes at a time.

During the study, while participants will be wearing the photobiomodulation device, they will be listening to the audio program, and they may be playing with their parent or the experimenter, using the toys of their choice (out of the many available in the experimenter’s office). The caregivers will be present during the experiment at all times. When the child and the parent arrive, they will be welcomed to the office, and introduced to the toys.

The child will be encouraged to play with toys and interact with the parent (or the experimenter). The children in the experimental condition will be asked to wear the device for no longer than 15 minutes. The children in the controlled condition will play for 30 minutes and wear the same device, without turning it on (the device won’t be turned on at that time). The total time in the office will be about 30 minutes (including playing).

If the child becomes uncomfortable, the parents will be able to leave the experiment without any punishment. No coercion or deception is involved in this study.

7.6 Pre and Post-Testing: CARS2 will be used for pretest and post-test. Please see attached a sample CARS 2 test. CARS 2 scores will be compared for analyses. **In addition, EEG will be collected from the participants in both Control and Experimental conditions pre and post -treatment (before Starting treatment in session 1 and in the end of treatment of Session 8). Mobile FDA approved EEG device Brain Scientific will be used to collect children's pre and post test EEG. There is no known danger of EEG collecting. In this study it will be using for measuring the efficacy treatment only.**

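### The EEG called post-treatment is fixed at Session 8, although the stated schedule implies about 16 sessions, and no planned EEG test clearly compares pre-to-post change between arms

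*Protocol*

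**What the plan says.** **Schedule.** Protocol section 1.0 opens with "The purpose of this 8-week open label feasibility study". Section 2.2 says "The children will wear the device for approximately 5-10 minutes, twice a week", and section 7.5 says "The treatment will take place twice a week for up to 30 minutes at a time". Section 2.2 also says this closely follows an earlier study of children with autism, which section 2.1 describes as two months of treatment at two sessions a week. Section 7.6 places the EEG recordings "before Starting treatment in session 1 and in the end of treatment of Session 8", labels them pre- and post-treatment, and says of the EEG: "In this study it will be using for measuring the efficacy treatment only". In the SAP (Primary Analyses) the final CARS was done right after the last treatment session.

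**Design.** Section 7.2 says "The placebo control condition will wear the same device, however the lights are not going to be turned on" and section 7.3 says "The experiment will use random assignment". Both arms have both EEG recordings.

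**EEG analysis.** After an undefined baseline normalization, section 7.7 plans three t-tests:

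- between arms before treatment, for each brainwave;
- between arms after treatment, for each brainwave;
- before against after, in the treatment arm only.

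The mixed-design ANOVA in the same section is for the quantitative data, defined there as total CARS2 scores. The available SAP sections contain no EEG analysis.

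**The concern.** There are two separate problems with the same endpoint.

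**Timing.** If both the stated schedule and the stated EEG session are followed, the recording called post-treatment falls about halfway through. It would then miss the second half of treatment and would not match the CARS visit in time, although both measures are called post-treatment.

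**Analysis.** The EEG is collected to measure efficacy, and a sham arm is recorded to show what changes without active light. Yet the only test that clearly uses each child's change leaves the sham arm out. These are children aged 2 to 6, most of them expected to be receiving behavioral therapy, so some change over eight weeks that both arms share is plausible. A paired test in one arm cannot separate that change from a treatment effect. No EEG test is named as the one that decides, so a significant one-arm result could be reported as efficacy.

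**Working it through.** **1. Session count.** Inputs: 8 weeks (section 1.0) and 2 sessions a week (sections 2.2 and 7.5).

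- Implied sessions: 8 × 2 = 16.
- Session 8 at two a week: 8 / 2 = end of week 4, with 8 of the 16 sessions given.
- For Session 8 to be the last, treatment would have to be weekly for 8 weeks or twice weekly for 4 weeks. Neither is stated in the available text.

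**2. The undefined normalization.** If it refers to each child's own pre-treatment recording, the post-treatment t-test becomes a comparison of change. But every child's pre-treatment value would then be the same (0 or 1, say), and the planned pre-treatment between-arm test would have nothing to compare. If it refers to some other baseline, the post-treatment test does not use the pre-treatment EEG. Either way the term needs a definition.

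**3. One-arm paired test with no treatment effect.** The documents give no EEG drift or correlation, so both are assumed. With n = 15, drift m in SD units and pre/post correlation r, the test has 14 df and noncentrality m√15 / √(2(1−r)). Example: m = 0.5 and r = 0.7 give 0.5 × 3.873 / 0.775 = 2.50. Chance of a significant result, two-sided 5%:

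| Drift (SD) | r = 0.3 | r = 0.7 |
|---|---|---|
| 0.2 | 0.094 | 0.154 |
| 0.3 | 0.150 | 0.287 |
| 0.5 | 0.332 | 0.643 |

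Under the same shared drifts, the between-arm post-treatment test rejected in 0.049 to 0.050 of simulated trials.

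For scale only, since this is CARS and not EEG: the SAP (Primary Outcome) shows the sham mean falling from 40.6 to 38.0 with baseline SD 7.2, and 2.6 / 7.2 = 0.36 SD. A drift of that size gives 0.197 (r = 0.3) to 0.391 (r = 0.7).

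**4. Power of the between-arm comparison.** 15 per arm, two-sided 5%, noncentral t with noncentrality d / (s√(2/15)). Here s = 1 for the post-only t-test (28 df), s = √(1−r²) for ANCOVA on the pre-treatment EEG (27 df) and s = √(2(1−r)) for a change score (28 df). All d and r are assumed.

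| d | Post-only | ANCOVA, r = 0.3 / 0.5 / 0.7 / 0.8 |
|---|---|---|
| 0.3 | 0.125 | 0.132 / 0.150 / 0.199 / 0.262 |
| 0.5 | 0.262 | 0.283 / 0.332 / 0.456 / 0.595 |
| 0.8 | 0.562 | 0.600 / 0.684 / 0.841 / 0.940 |

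Simulated ANCOVA that lets baseline differ by chance runs at most 1.6 points lower (0.668 against 0.684 at d = 0.8, r = 0.5), with type I error 0.048 to 0.051. A change score at d = 0.8 gives 0.432 / 0.562 / 0.779 / 0.917: below post-only when r is under 0.5, and below ANCOVA throughout this range. The effect detectable with 80% power is 1.06 SD post-only, against 1.01 / 0.92 / 0.76 / 0.64 SD with ANCOVA. With the SAP's 16 and 14 children, power changes by less than 1 point.

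Section 5.0 says of the sample size "These numbers will allow us to gain sufficient statistical power to detect small size systematic effect". At d = 0.3, the smallest effect tabulated, no analysis here exceeds 27% power.

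**The case against.** **Timing is not proven.** The 8 weeks describe the study and need not all be treatment. The same sentence calls the trial open label, which does not fit the randomized sham design described later, so it may not be reliable. Session 8 may be a slip for week 8. One part of the SAP was not available to this review. All of this stands, and it limits the finding to a conflict between sections. The two-month, twice-weekly study that section 2.2 says it follows nevertheless points the same way as the 16-session count.

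**A valid between-arm test is already planned.** Under random assignment the post-treatment t-test holds its 5% error rate, so adding the baseline is a matter of efficiency. This stands. So does the point that the one-arm test is offered as an addition, and that its significant results are correct detections of change over time; they mislead only if read as efficacy. With no deciding test named, the plan does not rule that reading out.

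**The gain may be small.** No EEG correlation is given. At r = 0.3 ANCOVA adds 0.7 to 3.9 points of power; at r = 0.2 it adds at most 1.6, and at r = 0 it loses about 0.1. This stands too, and it also shows that adjustment costs almost nothing.

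**EEG is supplementary in a feasibility study.** True, and for that reason the point is not rated higher. The protocol still gives the EEG an efficacy purpose.

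**Conclusion.** The concern holds on both counts and should be corrected; confidence is medium.

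On timing, the stated length and frequency imply 16 sessions against an EEG labelled post-treatment at Session 8. Whether that recording really falls mid-course depends on the session total, which the available text does not give.

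On analysis, no planned EEG test clearly compares pre-to-post change between arms. The one-arm test can be significant with no treatment effect in 9% to 33% of trials at r = 0.3 and 15% to 64% at r = 0.7, for assumed drifts of 0.2 to 0.5 SD. The valid post-only test gives up between 4 and 38 points of power at d = 0.8 as r goes from 0.3 to 0.8. These sizes rest on assumed EEG parameters. Baseline adjustment does not rescue the endpoint for a small effect.

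The consequence is confined to the EEG endpoint.

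**What to change.** - Reconcile the study length (section 1.0), the session frequency (sections 2.2 and 7.5) and the EEG session number (section 7.6), and state the total number of sessions.
- Define the second EEG as the one taken at the final treatment session, at the same visit as the final CARS, whatever its number. Label any earlier recording mid-treatment.
- Say which baseline the normalization uses.
- For each band, name one deciding comparison: ANCOVA of post-treatment EEG on arm, with pre-treatment EEG as covariate.
- Report within-arm change for both arms, descriptively only.
- Optional: label the EEG tests exploratory or apply Holm across bands, and take both recordings at the same point relative to device use. The number of bands is not stated; with 4 or 5 independent bands and no adjustment, the chance of at least one false positive among the post-treatment tests is 1 − 0.95⁴ = 0.19 or 1 − 0.95⁵ = 0.23.

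Cost: no extra recordings, only one visit definition, one defined term and revised analysis wording. ANCOVA uses one degree of freedom, and its gain is small if the pre/post correlation is low. Holm, if chosen, makes single bands harder to declare significant.

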9.0 Recommendation for Only One Parent Consent

Both this proposed study and the investigational device do not involve greater than minimal risk.

Rationale for the device:

Safety of Photobiomodulation: Photobiomodulation has been extensively studied on humans for more than 30 years, including its use for neurological conditions. There are several photobiomodulation products (for neurological conditions) that are on currently on the market (using both LED and Lasers). The consumers report no side-effects.

After more than three decades of research there are no known major side effects attached to photobiomodulation therapy.

Rare Minor Side effects for first time users only include: Tiredness (temporary) – probably due to the release of metabolites but the majority report a resurgence of energy. Headaches (temporary) – from the reactivation of neural connections and increased microcirculation.

Safety Issues of our product specifically: Our product emits non-laser based irradiation (incoherent light) with a low level energy intensity. Infrared emits non-laser based irradiation (incoherent light) with a low level energy intensity. We use 850 nm. The participants might perceive slight warm. No other perceptions will be produced by wearing the device. No feelings of discomfort are anticipated (the device is especially made for children, it's very comfortable and soothing to wear). There are no known side-effects of photobiomodulation (with 30 years of research and studies, including research on 5 year old children diagnosed with ASD).

Rationale for the study:

The study activities include: 1) wearing the device and / or 2) Listening to the audio program which provides language acquisition input or 3) free play while listening to nursery rhymes. In addition, the parents will be interviewed about the child's behavior on a weekly basis.

None of these activities present greater than minimal risk to the health and well-being of the participants.

